6.3. MISSING DATA

The handling of missing or incomplete data is described for each endpoint and data type (as needed) in Section 7 to 8.2.2.6.

6.4. ANALYSIS VISIT WINDOWS

Table 6 shows how data will be mapped to visit number prior to selection of records for analysis. All post-baseline visits, including unscheduled and early termination visits, will be mapped.

After mapping the data to the visits, the following rules will apply unless other handling is specified for a particular analysis.

- If multiple records are available within a single visit window, the record closest to the planned assessment day will be selected for analysis.
- If 2 records are equidistant from the target day, then the later record will be selected.
- If a subject has no record in an analysis window, the data will be considered missing at that visit.

Table 6 Analysis Visit Windows

Study Day Window	Scheduled day	Scheduled Visit/Week
Day 1 - 63	Day 42	Visit 5/Week 6
Day 64 - 105	Day 84	Visit 6/Week 12
Day 106 - 147	Day 126	Visit 7/Week 18
Day 148 - 210	Day 168	Visit 8/Week 24
Day 211 - 294	Day 252	Visit 9/Week 36
Day 295 - 420	Day 336	Visit 10/Week 48
Day (xx*7-83) - minimum (xx*7+84, End of Treatment Visit date)	Day (xx*7)	Visit /Week xx, where xx is every 24 weeks.
> End of Treatment Visit date + 7	End of Treatment Visit + 28	Follow-up Visit

If there are multiple end of treatment visits, the one closest to the last dose date will be used. If multiple records are equidistant from the last dose date, the later one will be used. Analysis visit windows will be used for all lab, vital sign, and ECG data.

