5.2.5 Rescue Medications for Hyperglycemia

During the treatment period subjects will be advised to conduct daily fasting SMBG measurements. Blood glucose values collected via SMBG will be evaluated at study visits by the investigator. In addition, hyperglycemia will be monitored by FPG measurement at each study visit. HbA1c values will also be available to the investigator for decision-making regarding the need for rescue medication.

If hyperglycemia is identified through SMBG or FPG measurements, the investigator will determine whether the subject has fasted for a minimum of 10 h prior to the morning blood draw to ensure that the FPG value is truly a fasting sample. If proper fasting has not occurred, the subject will be asked to return for a repeat blood test within a week.

During the first 24 weeks of the treatment period, hyperglycemia should be managed with diet and exercise counseling and only with changes in the medical therapy if the investigator feels it is necessary for the well-being of the subject. Intensification of the antidiabetic regimen should adhere to the following guidelines upon the report by a study subject of two fasting blood glucose self-measurements exceeding the following values on consecutive days: (i) ≥ 270 mg/dL (15 mmol/L) from week 1 to week 6; ≥ 240 mg/dL (13.3 mmol/L) between week 6 and week 12; and ≥ 200 mg/dL (11.1 mmol/L) between week 12 and week 24. After 24 weeks changes to the medical therapy for hyperglycemia should occur at the discretion of the investigator based on SMBG, FPG, and HbA1c information using local standards of care for subjects with T2DM. If a rescue medication for hyperglycemia is to be prescribed, a blood sample must be drawn prior to the administration of the rescue medication so that a final HbA1c value can be determined for the HbA1c efficacy analyses.

The investigator may provide rescue treatment with any approved medication for diabetes that is not otherwise contraindicated, with the exception of an SGLT2 inhibitor. Dose or frequency increases in OHA or insulin regimens prescribed prior to screening will be considered rescue medication. During the treatment period, increments or decrements in the doses of OHA or insulin must be documented in the concomitant medications CRF.

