7 STUDY ACTIVITIES

The study activities at each clinic visit listed below are presented in [Appendix 1](#). The required laboratory tests scheduled at each visit are listed in [Appendix 2](#). Detailed study procedures are described in [Section 6](#).

A visit window of ± 3 days is allowed for all visits except visit V3. Visit 3 is the day of randomization and the basis for the visit window.

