3.10. STUDY PROCEDURES AND FLOWCHART

The study activities at each clinic visit are presented in Table 2 and Table 3. The schedule of laboratory tests is presented in Table 4.

A visit window of ± 3 days is allowed for all visits except Visit 3. Visit 3 is the day of randomization and the basis for the visit window.

The study staff will contact each subject prior to a scheduled clinic visit to confirm the time of the visit and to remind the subject of proper fasting practice. A subject must be queried to assess compliance with a minimum 10 hours fast prior to blood draw to ensure the FPG and triglycerides values can be accurately determined. If a subject has not fasted for 10 hours, the subject must return as soon as can be arranged (within 1 week) to provide a specimen after proper fasting. Urine samples will be transported to the central lab for urinalysis.

Table 2 Schedule of Events from Screening to Week 48

Procedure	Screening	Run-in	Treatment Period							
	V1	V2	V3	V4	V5	V6	V7	V8	V9	V10
Visit number	V1	V2	V3	V4	V5	V6	V7	V8	V9	V10
Time to Randomization Visit (weeks) ¹	-2 to -5	-2	0	2	6	12	18	24	36	48
Type of visit ²	C	C	C	P	C	C	P	C	C	C
Informed Consent	X									
Screening for I/E criteria	X		X							
Demographics and medical history	X									
Diet & exercise counseling ³		X								
Physical exam ⁴	X		X			X		X	X	X
Weight and height ⁵	X	X	X		X	X		X	X	X
Diary & glucometer record review ⁶		X	X	X	X	X	X	X	X	X
Dispense Run-in Medication		X								
Randomization			X							
Vital signs	X		X		X	X		X	X	X
ECG	X		X					X		X
Dispense study medication ⁷			X			X		X	X	X
Blood draw for clinical lab test ⁸	X		X		X	X		X	X	X
Population PK sampling ⁹					X	X				
Urine collection ¹⁰	X		X		X	X		X	X	X
AE and potential DKA		X	X	X	X	X	X	X	X	X
Con Med		X	X	X	X	X	X	X	X	X

Table 3 Schedule of Events after Week 48 to End of Study

Procedure	Treatment Period			Follow Up
	Visit number	V 12, 14, 16, 18, etc.	EV	FU
Time to Randomization Visit (weeks) ¹	V 11, 13, 15, 17, etc. 60, 84, 108, 132, 156, etc.	V 12, 14, 16, 18, etc. 72, 96, 120, 144, 168, etc.	End of treatment visit	4 weeks after EV
Type of Visit ²	P	C	C	C
Informed Consent				
Screening for I/E criteria				
Demographics and medical history				
Diet & exercise counseling ³				
Physical exam ⁴		X	X	X
Weight and height ⁵		X	X	X
Diary & glucometer record review ⁶	X	X	X	X
Dispense Run-in Medication				
Randomization				
Vital signs		X	X	X
ECG		X	X	X
Dispense study medication ⁷		X		
Blood draw for clinical lab test ⁸		X	X	X

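### SAP 6.4 picks the laboratory record nearest the target day without regard to fasting, so where a non-fasted FPG has been repeated fasted it usually keeps the non-fasted value

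*Combined protocol and SAP*

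**What the plan says.** SAP 6.4 first assigns records to windows: "All post-baseline visits, including unscheduled and early termination visits, will be mapped". It then chooses one record per window: "If multiple records are available within a single visit window, the record closest to the planned assessment day will be selected for analysis". Ties are broken by date: "If 2 records are equidistant from the target day, then the later record will be selected". The scope is wide: "Analysis visit windows will be used for all lab, vital sign, and ECG data". The section leaves room for exceptions, since "the following rules will apply unless other handling is specified for a particular analysis". However, neither SAP 8.2.2.2 (FPG over time) nor SAP 9.4 (laboratory evaluations) gives an exception for fasting status. The LDL-C algorithm in SAP 9.4 turns on screening triglycerides, not on fasting.

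Protocol 5.2.5 has the investigator check fasting once hyperglycemia has been identified through SMBG or FPG: "If proper fasting has not occurred, the subject will be asked to return for a repeat blood test within a week". Protocol 6.7.2.1 and SAP 3.10 say of a subject who has not fasted for 10 h that "the subject must return as soon as can be arranged (within 1 week) to provide a specimen after proper fasting".

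Other passages aim to prevent a non-fasted draw. Protocol 3.2.2 and footnote 8 of Appendix 1 require the 10 h fast to be confirmed before blood is taken. The visit lists in Protocol 7.3.1 to 7.4.1 direct clinic-visit draws to subjects who have completed the fast.

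**The concern.** When the check in Protocol 5.2.5 is prompted by an FPG result, the first glucose value already exists. The repeat is obtained because that value is not valid as a fasting measure. The scheduled visit sits near the target day and the repeat comes later, so a rule based only on nearness tends to prefer the wrong record.

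At stake is whether FPG in SAP 8.2.2.2 is a fasting measure at those visits. Baseline has a related weakness. SAP 6.2.1 takes the last non-missing value on or before the first-dose day. If the V3 draw proves non-fasted, that value stays as baseline and enters every change score for the subject, because a repeat on a later day would normally be post-dose.

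**Working it through.** The plan states no figure on this point, so there is none to reproduce. The check asks which record the rule selects when a visit has both a non-fasted first draw and a later fasted repeat.

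**Inputs from the documents**
- First-draw offset v from the nominal visit day: −3 to +3 days (Protocol Section 7: "A visit window of ± 3 days is allowed for all visits except visit V3").
- Repeat delay r: within a week, taken as 1 to 7 days (Protocol 5.2.5, 6.7.2.1).
- Target days and windows: SAP Table 6. Ties go to the later record.
- Day numbering: the first dose is Study Day 1 (SAP 6.2.3) and is given at V3 (Protocol 5.3), from which visits are timed. The week 24 visit is therefore nominally on Day 1 + 168 = Day 169, while Table 6 targets Day 168. This supports a one-day shift.

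**Assumed, because the documents do not say:** the distributions of v and r.

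**Do both records share a window?** The repeat falls at most 3 + 7 = 10 days after the target, or 11 with the shift. The shortest upper margin in Table 6 is 63 − 42 = 21 days, so yes. One exception: after week 48 the window is capped at the End of Treatment visit date and follow-up starts more than 7 days after it. A repeat 1 to 7 days after that visit falls in neither, and the first record is again the one left.

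**Which is kept?** The non-fasted record is selected when |v| < |v + r|. For v ≥ 0 this always holds. For v < 0 it holds only when r > 2|v|. With r uniform on 1 to 7 and no shift:
- v = 0, 1, 2, 3: 7/7 each, 28 pairs in all
- v = −1: r = 3 to 7, 5/7 = 71.4%
- v = −2: r = 5 to 7, 3/7 = 42.9%
- v = −3: r = 7, 1/7 = 14.3%

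Total (28 + 5 + 3 + 1)/49 = 37/49 = 75.5%. With the shift, offsets run from −2 to +4 and the total is (35 + 5 + 3)/49 = 43/49 = 87.8%.

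| First-draw days | Repeat delay | Centred on target | Centred one day later |
|---|---|---|---|
| uniform | uniform 1–7 | 75.5% | 87.8% |
| uniform | 1–7, weights falling 7 to 1 | 68.4% | 82.1% |
| uniform | uniform 1–3 | 13/21 = 61.9% | 16/21 = 76.2% |
| uniform | next day | 4/7 = 57.1% | 5/7 = 71.4% |
| triangular (1,2,3,4,3,2,1) | uniform 1–7 | 82.1% | 92.9% |
| triangular | 1–7, weights falling 7 to 1 | 75.4% | 89.3% |
| triangular | uniform 1–3 | 68.8% | 85.4% |
| all on nominal day | any | 100% | 100% |

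**After the fix:** with non-fasted records removed first, 0% of visits that have a fasted repeat in the window would use the non-fasted value.

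**The case against.** The strongest reply is that the protocol is built to avoid the two-record visit. If the fast is confirmed before the draw, an unfasted subject has no first FPG. The return visit in Protocol 6.7.2.1 and SAP 3.10 is then a deferred draw, and the rule selects the only record there is. Only Protocol 5.2.5 clearly implies a pair, and only after the pre-draw check has failed. Protocol 6.7.7 also allows local analysis at unscheduled visits, and the documents do not say whether local values enter the FPG analysis. All of this stands as a limit on frequency. It does not remove the gap, because Protocol 5.2.5 plans for exactly this case and the SAP's stated rule then usually resolves it the wrong way.

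The percentages are also open to challenge. Returning as soon as can be arranged favours short delays and hence lower shares, and for draws two or three days early the fasted repeat is usually kept. That is why a range is given and no single figure is claimed.

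The extension to lipids is weaker. Protocol 5.2.5 does not say that lipids are redrawn, and lipids are not scheduled at week 6 (Protocol Appendix 2). It applies only where a fasted lipid repeat exists.

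**Conclusion.** The gap is real and minor. Where a non-fasted FPG and its fasted repeat share a window, SAP 6.4 keeps the non-fasted value more often than not: about 57% to 100% across the averaged scenarios, with 76% and 88% as the uniform-timing results without and with the one-day shift. These shares rest on assumed timing and apply only to two-record visits, which should be uncommon.

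Two stronger readings are tempting and unsupported. First, a reader might infer that much of the FPG endpoint is non-fasting. The documents give no frequency of non-fasted draws, and their controls point to a low one.

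Second, since the Protocol 5.2.5 check follows a high value, a reader might infer that the error favours the drug. Suppose such visits make up 1–3% of bexagliflozin and 2–8% of placebo records, the non-fasting excess is 40–80 mg/dL, and 0.8 of the pairs are resolved wrongly. All of these are assumptions. Pairing low with low and high with high gives 0.8 × (0.02 − 0.01) × 40 = 0.3 to 0.8 × (0.08 − 0.03) × 80 = 3.2 mg/dL in the drug's favour. The same inputs over their full range give 0.8 × (0.02 − 0.03) × 80 = −0.6 to 0.8 × (0.08 − 0.01) × 80 = +4.5 mg/dL. Size and direction are therefore unknown.

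FPG over time is exploratory, with nominal p-values (SAP 8.2.2). The primary HbA1c analysis and the key secondary endpoints (HbA1c in insulin users, body weight, SBP) are not affected.

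**What to change.** - Add to SAP 6.4 that FPG records known to be drawn after less than a 10 h fast are excluded before the nearest-day rule is applied. The fasted repeat is then used, or the visit is missing if there is none.
- Apply the same exclusion to triglycerides and calculated LDL-C where they were drawn.
- For baseline FPG, use the last fasted value on or before the first dose, for example the screening value, and never a post-dose repeat.
- State how a fasted repeat of the End of Treatment sample is mapped, and whether local laboratory repeats enter the analysis.
- Reconcile the repeat-test text in Protocol 5.2.5 with the instructions to draw only from fasted subjects, and the approximate 10-hour fast in SAP 9.4 with the 10-hour minimum in Protocol 6.7.2.1 and SAP 3.10.

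The cost is a short SAP addition, a few more missing FPG values, and the need to carry fasting status in the analysis dataset. The protocol requires the fasting query, but no passage says that the answer is stored with each record, so this should be confirmed first.

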7.5 Discontinuation of Investigational Product Administration

Subjects who discontinue the investigational product administration early but are willing to remain in the study to allow safety information to be collected should complete the End of Treatment visit procedures. Safety data may be documented following the scheduled clinic visit and/or phone interview procedures as much as possible without the study drug

dispensation and accountability procedures. Alternative follow up methods to allow safety assessment to be recorded may be implemented as unscheduled visits.

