8.1.1. Primary Efficacy Analysis

Let $\mu_{\text{Bexagliflozin}}$ and μ_{PBO} represent the mean changes from baseline in HbA_{1c} at Week 24 for bexagliflozin and placebo arms, respectively. The following hypotheses will be tested:

$$H_0: \mu_{\text{bexagliflozin}} - \mu_{\text{placebo}} \geq 0$$

$$H_a: \mu_{\text{bexagliflozin}} - \mu_{\text{placebo}} < 0$$

Missing data will be imputed via multiple imputations, following which the MMRM will be repeated on the complete datasets with results combined across complete datasets using standard multiple imputations techniques; HbA_{1c} values collected after the start of intensification of hypoglycemic agent will not be excluded. A pattern-mixture model will be used to explore the impact of the missing data. Imputation will be conducted within each treatment arm and subgroup (treatment completer vs. treatment terminated early) under the assumption that non-adherent subjects with missing data will follow the same trajectory of non-adherent subjects with values observed. All efforts will be made to retain subjects in the study. If treatment is discontinued, subjects are encouraged to remain in the study and complete all scheduled visits, including final follow-up visit. However, with all efforts, insufficient values may be available for reliable imputation. This analysis will be performed only if at least 5 subjects in each treatment arm completed scheduled week 24 visit after treatment is stopped. This number is chosen to allow sufficient data to establish a regression model for imputation. For this analysis, the following three-step approach outlined below will be used:

- a. Non-monotone (intermediate visits) missing data will be imputed first using the Monte Carlo Markov Chain (MCMC) method under the MAR assumption in all treatment arms (using the MCMC statement in PROC MI). Multiple chains option

(CHAIN=MULTIPLE option in the MCMC statement of PROC MI) will be used. For the non-monotone imputation of the HbA_{1c} missing data, a multivariate normal model will be used including variables for the HbA_{1c} at baseline and all post-baseline visits within each treatment group. Five hundred imputed datasets will be generated.

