8.2.2.2. Changes from baseline in HbA_{1c} and FPG over time

Of interest is the difference between treatments on these two endpoints across all post-baseline time points with sufficient number of values. If for any treatment arm, less than 20 subjects completed the assessment in the analysis visit window, the visit will not be included in the analysis. Both endpoints will be analyzed using MMRM model with the change from baseline values across all post-baseline visits used as dependent variable. The fixed effect will include baseline eGFR (≥ 60 or < 60 mL min⁻¹ [1.73m]⁻²), baseline BMI ($<$ or ≥ 25 kg m⁻²), and history of heart failure (yes or no), insulin use or not, treatment, visit, treatment and visit interaction, other hypoglycemic agent use (no change, after relaxation, or after intensification), treatment and other hypoglycemic agent use interaction, and baseline value. For each endpoint, treatment difference in least squares means will be estimated by visit from the model with the corresponding p-values and the two-sided 95% CIs of the difference between treatments.

Analysis of HbA_{1c} over time will also be conducted for subjects who have been prescribed insulin or sulfonylurea to control their diabetes.

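### SAP Table 6 closes every window from week 72 on at the End of Treatment visit, so values taken after early drug stop leave their scheduled weeks; for weeks 6 to 48 it leaves an overlap with Follow-up unresolved

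*Combined protocol and SAP*

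**What the plan says.** SAP 6.4, Table 6, has three kinds of row. Weeks 6 to 48 are fixed ranges of study days; week 24 is days 148 to 210 and week 48 is days 295 to 420. From week 72 on, every 24 weeks, the window is "Day (xx*7-83) - minimum (xx*7+84, End of Treatment Visit date". The Follow-up row takes any day "> End of Treatment Visit date + 7", has a target of EOT + 28 days, and has no upper limit.

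On the choice of anchor, the SAP says: "If there are multiple end of treatment visits, the one closest to the last dose date will be used". Where several records share a window, the one nearest the target day is kept. A window with no record is treated as missing. The windows apply to laboratory, vital-sign and ECG data.

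Protocol 7.5 covers the subjects at issue: "Subjects who discontinue the investigational product administration early but are willing to remain in the study". It has them go through the EOT assessments and then expects visits to go on: "Safety data may be documented following the scheduled clinic visit and/or phone interview procedures as much as possible". SAP 8.1.1 likewise encourages these subjects to attend all remaining scheduled visits.

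Two sets of analyses depend on such values. The primary HbA1c imputation uses them, with the condition "This analysis will be performed only if at least 5 subjects in each treatment arm completed scheduled week 24 visit after treatment is stopped". The over-time models for HbA1c and FPG (SAP 8.2.2.2) state: "Both endpoints will be analyzed using MMRM model with the change from baseline values across all post-baseline visits used as dependent variable". SAP 8.2.2.3 says the same for SBP and weight.

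**The concern.** For a subject who completes treatment, the EOT visit comes at the end of the trial, and capping the last window there is sensible. For a subject who stops drug early and stays, the anchor is the visit at drug stop, possibly years before the last study visit. The cap then removes every later scheduled window from week 72 on, although the protocol asks for those visits and the over-time models are described as using all of them. One model would include off-drug values up to week 48 and none after it. The late estimates would describe subjects still on drug, without the SAP saying so.

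For weeks 6 to 48 the problem is different. A value taken more than seven days after EOT fits two rows. The selection rules choose between records within one window; they do not say where a single record belongs when it fits two. That matters most at week 24, where the primary imputation relies on off-drug HbA1c.

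**Working it through.** The documents give no figure to reproduce here, so the check applies Table 6 literally.

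**Inputs.** The windows and anchor rule come from SAP 6.4. Scheduled days are 7 × week: 168, 252, 336, 504, 672 and 840 for weeks 24, 36, 48, 72, 96 and 120. Protocol 7.5 gives no day for the EOT procedures after early stop. I take them to occur at or soon after drug stop, which the closest-to-last-dose rule supports.

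**Week-72 window.** The lower bound is 72 × 7 − 83 = 421. The uncapped upper bound is 72 × 7 + 84 = 588.
- EOT on day 210: day 421 to min(588, 210) = 210. The window is empty.
- EOT on day 500: day 421 to min(588, 500) = 500. A day-504 value is too late for week 72. It is also too early for Follow-up, which needs a day after 507, so it fits no row. Yet SAP 6.4 says that all post-baseline visits will be mapped.

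**Rows met by each scheduled day** (FU = Follow-up):

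| EOT day | 168 | 252 | 336 | 504 | 672 | 840 |
|---|---|---|---|---|---|---|
| 100 | Wk 24 and FU | Wk 36 and FU | Wk 48 and FU | FU only | FU only | FU only |
| 300 | Wk 24 | Wk 36 | Wk 48 and FU | FU only | FU only | FU only |
| 500 | Wk 24 | Wk 36 | Wk 48 | none | FU only | FU only |
| 900 (completer) | Wk 24 | Wk 36 | Wk 48 | Wk 72 | Wk 96 | Wk 120 |

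**What Follow-up keeps.** It retains one record per subject, the nearest to EOT + 28. With EOT on day 210 the target is day 238, so the values on days 504, 672 and 840 compete for a single place and at most one of them can be used.

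**Why a cap exists.** For the completer with EOT on day 900, the follow-up visit falls on day 928. The week-144 window opens on 144 × 7 − 83 = 925, so without a cap an off-drug follow-up value would be labelled week 144. The cap is right for the end-of-trial EOT visit and wrong for one at early drug stop.

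**Which analyses are affected.** SAP 8.2.2.2 decides whether a visit enters the model by counting subjects assessed in its analysis window, so Table 6 governs that model directly. SBP and laboratory data are covered by SAP 6.4. Two limits apply. SAP 9.5 describes the vital-sign summaries by nominal visit, which may not mean Table 6. Body weight is not named among the windowed data, and protocol 6.4 lists only blood pressure and heart rate as vital signs.

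**Scale.** The only rate stated is 6.5% per year, for premature withdrawal or early termination from the study. No rate is given for stopping drug while staying in.

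**The case against.** The strongest reply is that nothing confirmatory is lost. The primary endpoint and all three key secondary endpoints lie at week 24 or 48, where the windows carry no EOT cap. SAP 8.1.1 counts subjects who completed the scheduled week-24 visit off drug, its imputation separates those who completed 24 weeks of treatment from those who did not, and SAP 12 says that the primary analysis uses retrieved dropouts. All of this requires off-drug week-24 HbA1c to stay at week 24. The week-72+ models are exploratory, with nominal p-values. The HbA1c and FPG model also adjusts for later changes in other hypoglycemic agents, so it was never a clean treatment-policy comparison. This stands, and it limits the severity.

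A reader might infer that Table 6 moves week-24 values to Follow-up, empties the retrieved-dropout group and triggers the fallback to MMRM on available data. The documents do not support that. It would take a programmer choosing the one reading that defeats SAP 8.1.1.

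A reader might also scale the 6.5% rate up: 1 − 0.935² = 12.6% and 1 − 0.935³ = 18.3%, or about 208 to 301 of 1,650 subjects over two to three years. That borrows a study-withdrawal rate for a different group. Subjects who leave the study supply no later records to mis-map, and those who stop drug late have few.

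It could also be said that on-drug values were intended for the late visits. Nothing in SAP 8.2.2 says so, and the week 6 to 48 windows do not work that way. Intent in SAP 8.1.1 is also not a mapping rule, so the overlap still needs a sentence.

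**Conclusion.** The point holds in two parts. From week 72 on, Table 6 as written removes retained early stoppers' HbA1c, FPG, SBP and laboratory values from their scheduled windows. They go to Follow-up, or to no row if taken one to seven days after EOT. This conflicts with over-time models said to use all post-baseline visits. For weeks 6 to 48 nothing is removed, but records more than seven days after EOT meet two rows with no stated precedence. At week 24 that is a risk of misreading, not a loss that the rule produces.

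The definite effect is confined to the exploratory over-time models and to the by-visit safety summaries that use Table 6. Its size cannot be derived from the documents. The conclusion assumes that EOT procedures after early stop take place near the last dose and that at least some of these subjects attend later visits. An effect on body weight would be an inference. This should be fixed, but it is not a condition for a valid primary analysis.

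**What to change.** In Table 6:
- Assign records to scheduled-week windows by study day for every subject still in the study, on or off drug, and state that these windows take precedence over Follow-up. Say explicitly that off-drug week-24 HbA1c stays at week 24.
- Remove the EOT-date cap for subjects who stop drug early, and keep it for the end-of-trial EOT visit.
- Restrict the Follow-up row to the follow-up visit recorded as such on the CRF.
- Carry on- or off-drug status as a separate flag, so that an on-drug summary can still be produced if wanted.
- State whether body weight uses these windows.

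The cost is SAP wording and one programming rule before database lock, with no new data. The late over-time summaries will then include off-drug values and should be described that way.
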